### Planned Accrual Estimates

Racial Categories	DOMESTIC PLANNED ENROLLMENT REPORT				
	Ethnic Categories				
	Not Hispanic or Latino		Hispanic or Latino		Total
	Female	Male	Female	Male	
American Indian/Alaska Native	0	0	0	0	0
Asian	0	0	0	0	0
Native Hawaiian or Other Pacific Islander	0	0	0	0	0
Black or African American	1	5	0	0	6
White	7	9	1	1	18
More Than One Race	0	0	0	0	0
Total	8	14	1	1	24

Racial Categories	INTERNATIONAL (including Canadian participants) PLANNED ENROLLMENT REPORT				
	Ethnic Categories				
	Not Hispanic or Latino		Hispanic or Latino		Total
	Female	Male	Female	Male	
American Indian/Alaska Native	0	0	0	0	0
Asian	0	0	0	0	0
Native Hawaiian or Other Pacific Islander	0	0	0	0	0
Black or African American	0	0	0	0	0
White	0	0	0	0	0
More Than One Race	0	0	0	0	0
Total	0	0	0	0	0

### 13.4 Primary Objective, Endpoint(s), Analysis Plan

**Primary Endpoint:** To a direct comparison of the pharmacological effect on cGMP levels for dolcanatide arm vs. placebo, where this effect is defined below:

**Pharmacological Effect on cGMP levels:** Arithmetic difference in mean cGMP levels before and after 7 days of dolcanatide from subject biopsies. This represents the increase in cGMP stimulated by 7 days dolcanatide in an individual subject. The mean cGMP value will be calculated based on 8 biopsies from the rectum assessed at each time point.

With a sample size of 12 per arm, we'd have 80% power to detect a significantly increased Pharmacological Effect of the continuous cGMP results for dolcanatide vs. placebo, assuming a 1-sided significance level of 5%. The study would be powered to detect an effect size of 1 (i.e. [difference in means]/SD = 1). Prior data from one of the active doses for the MAY2012-00-01 study found a difference in means of around 4 for the PD effect (5 vs. 1), with an SD of around 4 as well. This would be an example of an effect size of 1 (4/4). Given this prior data, we believe an effect size of 1 is achievable. We'll also report the 2-sided 95% confidence intervals as well for final results. If the cGMP values are not normally distributed, a transformation to a variable with a normal distribution will be performed. See the detailed calculations below:

Let  $x_{zij}$  = baseline cGMP level for person  $i$  in randomization group  $z$  with replicate  $j$ .

$$x_{zimean} = \sum_j x_{zij} / 8 = \text{mean baseline level}$$

Let  $y_{zij}$  = day 7 cGMP level for person  $i$  in randomization group  $z$  and replicate  $j$ .

$$y_{zimean} = \sum_j y_{zij} / 8 = \text{mean baseline level}$$

Let  $i$  index person and  $z = 0, 1$  index group.

$$\text{Let } d_{zi} = (y_{zimean} - x_{zimean}) = \text{effect in person } i \text{ in group } z.$$

$$d_{zmean} = \sum_i d_{zi} / 12 = \text{mean effect over all persons in group } z$$

$$\text{var}_z = \sum_j (d_{zi} - d_{zmean})^2 / 11$$

$$\text{var}_{zmean} = \text{var}_z / 12 = \text{variance of mean effect in group } z$$

$$\text{dif} = d_{1mean} - d_{0mean}$$

$$\text{vardif} = \text{var}_{1mean} + \text{var}_{0mean}$$

$$\text{sedif} = \text{sqrt}[\text{vardif}].$$

The final result is dif with two-sided 95% confidence interval, dif-1.96 sedif, dif+1.96 sedif.

The sample size per randomization group is:

$N = (z_\alpha + z_{\text{power}})^2 \text{ vardif} / \text{dif}^2$ , where  $z_\alpha$  and  $z_{\text{power}}$  are z-statistics for type I error and power.

The anticipated values are

$$\text{var}_{1mean} = 4^2 \text{ and } \text{var}_{0mean} = 4^2, \text{ and } \text{dif} = 4;$$

Substituting into the formula, gives sample size for one arm as

$$N = (z_\alpha + z_{\text{power}})^2 * (32 / 16) = ((z_\alpha + z_{\text{power}})^2) * 2$$

It is important to keep type error at .05 for the analysis. Let us say it is one-sided. Suppose the power is .8 Then  $N = ((1.645 + .84)^2) * 2 = 12.35$ , which rounds to 12 per arm.

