The safety and efficacy to induce a PD effect on cGMP concentrations in colorectal mucosa of a different GCC agonist was evaluated in a double-blind, placebo-controlled study (MAY2012-00-01). The trial involved 6 normal healthy volunteers. Three received a single dose of 0.870 mg of a GCC agonist, and 3 received placebo, daily for seven consecutive days. The last dose was administered while the subjects were undergoing bowel prep for colonoscopy. Eight biopsies were collected from each of the cecum, transverse colon and rectum, by colonoscopy following standard colonoscopic bowel preparation, before the first dose and after the last dose of experimental agent. A PD effect on cGMP concentrations was observed in mucosae collected from the cecum, transverse colon, and rectum in two of three patients receiving the active GCC agonist, compared to subjects receiving placebo. Effects of this GCC agonist on cGMP concentrations were associated with increases in phosphorylation of VASP, a downstream protein target of cGMP signaling, and a decrease in epithelial cell proliferation quantified by ki67 immunohistochemistry. **There were no safety concerns observed during the trial.** The most common adverse event in subjects receiving the previous GCC agonist was diarrhea.

This study was extended to a second phase to determine if lower doses of the previous GCC agonist could be used to induce rectal cGMP responses. The first stage involved 6 normal healthy volunteers. Three received a single dose of 0.870 mg of the GCC agonist, and 3 received placebo, daily for seven consecutive days. The last dose was administered while the subjects were undergoing oral bowel prep. Eight biopsies were collected from the rectum by sigmoidoscopy following standard colonoscopic bowel preparation, before the first dose and after the last dose of experimental agent. A PD effect on cGMP concentrations was observed in mucosae collected from the rectum in two of three participants receiving active agent, compared to participants receiving placebo. The second stage of this study reproduced the first stage, except that participants were prepared for sigmoidoscopy using either tap water or PEG enemas. Using either of these approaches, a PD effect on cGMP concentrations was **not** observed in mucosae collected from the rectum in any participants receiving active agent.

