6.8.2.6 Stratification Factors: None

## 6.9 Blinding and Unblinding Methods

Pre-registered participants will be assigned a unique subject number, e.g., an 8-character identification number, e.g. CPN00001. Participants will be randomized at registration on Day 1 to receive active intervention or placebo after they have satisfied the inclusion/exclusion criteria. For each participant, the sequence assignment will be determined according to a prepared randomization schedule at the time of registration/randomization. The assigned study agent bottle number generated for each randomized participant will be sent to the Thomas Jefferson University personnel. Pharmacy personnel will not be blinded to intervention arm assignment.

The study will be double-blinded until after specimen analysis to ensure that the participants, investigators, and clinic staff are unaware of the dosing assignment and to minimize potential for bias in study assessments or in reporting of AEs.

There are two distinct situations in which it will be deemed appropriate to break the randomization assignment for participants enrolled onto this current trial:

- In the event of an *emergency* for an individual participant.
- Serious Adverse Event (SAE) that fulfills the criteria for expedited reporting to the FDA.

In these situations, Participating Organization personnel may assume the participant is on active agent and call the CPN Registration Office within one business day to receive unblinding information. The study name/number, participant identifier, and participant initials will be required to break the randomization code. Thomas Jefferson University personnel are responsible for notifying the medical monitor at DCP, NCI of the unblinding event.

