### **10.2 Collection and Handling Procedures**

- Eight mucosa biopsies will be collected from the rectum (at or just above the inferior valve of Houston) pre-intervention and post-intervention (Day 7, after administration of dolcanatide or placebo for 7 days).
- Five biopsies will be flash-frozen in liquid nitrogen individually in a screw cap vial and provided a sample-specific ID. Among the 5 biopsies, 2 of them will be evaluated for cGMP concentration. Frozen tissues will be transferred and stored at -80°C in [name] laboratory. In addition, 3 biopsies will be flattened immediately and fixed in 10% formalin within 2 min of collection in pre-labeled cassettes with tracking information provided, for future Ki67 immunohistochemistry analysis, if necessary.
- After formalin fixation overnight, samples will be transferred to 70% ethanol and sent to the Pathology Department for routine tissue processing. Processed tissue will be transferred to [name] laboratory for biomarker studies.
- All specimens from the each biopsy will be put into pre-labeled containers separated for analysis.
- Containers will be labeled with study number, registration number, date/time of collection, anatomical location and biopsy number. For example, 000-D7-Rec-1.
- Specimen manifest will be sent by email to the Biospecimens Resource Manager at the time of shipment.

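### Section 13.4 uses baseline cGMP only by subtraction; prespecified baseline adjustment with t-based inference, on a scale fixed in advance, is a cheap possible improvement

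*Combined protocol and SAP*

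**What the plan says.** **Use of baseline.** Section 13.4 defines the pharmacological effect as the "Arithmetic difference in mean cGMP levels before and after 7 days of dolcanatide from subject biopsies". Each person's effect is d = day-7 mean minus baseline mean. The result is dif, the difference between the arm means of d, with interval dif ± 1.96 sedif. Sections 13.1 to 13.10 name no baseline covariate, ANCOVA or other regression for this endpoint.

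**Scale.** The same section adds: "If the cGMP values are not normally distributed, a transformation to a variable with a normal distribution will be performed". It names neither the check nor the transformation.

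**Power.** With 12 per arm, Section 13.4 claims "80% power to detect a significantly increased Pharmacological Effect of the continuous cGMP results" at one-sided 5%, for a difference of 4 and an SD of 4.

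**Randomization.** Item 6.8.2.6 reads "Stratification Factors: None". That is no fault; it only means that baseline cGMP is left to chance.

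**Replicates.** Section 13.4 states: "The mean cGMP value will be calculated based on 8 biopsies from the rectum assessed at each time point". Section 10.2 states: "Among the 5 biopsies, 2 of them will be evaluated for cGMP concentration".

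**The concern.** Subtracting baseline fixes its slope at 1. If the true slope of day-7 on baseline cGMP is well away from 1, the change score carries avoidable noise. Baseline biopsies are taken before the first dose, so baseline is a legitimate covariate that is already paid for. The trial also has little slack: the formula gives 12.35 per arm and the plan rounds down to 12.

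Two neighbouring matters bear on any adjustment. The scale is open, and a fitted slope is more sensitive to skew than a plain difference. The interval uses a normal quantile with an SE estimated from 24 people. At stake are some points of power and the accuracy of the reported interval, not the direction of the estimate.

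**Working it through.** **Inputs from Section 13.4:** difference 4; SD 4, read as the SD of d because the formula for var_z is the variance of d; 12 per arm; one-sided 5%. Section 13.6 expects no drop-outs. **Assumed, because not given:** rho from 0.3 to 0.9, and the ratio of day-7 to baseline SD.

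**1. The plan's own figure.** N = 2 × (1.645 + 0.84)² = 12.35, as printed. At 12 per arm, power is 78.9% by normal approximation and 76.7% for a t test on 22 df (critical value 1.717). The 76.7% is the comparator below.

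**2. Unbiasedness.** In simulation with normal data and equal SDs, the change-score estimate averaged 3.98 to 4.00 when the truth was 4, and between −0.008 and 0.004 when the truth was 0. Its t test rejected in 4.95% to 5.14% of null trials.

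**3. The interval.** With equal arm sizes, sedif equals the pooled standard error. Under equal variances the reference is t on 22 df, with quantile 2.074. An interval of ±1.96 sedif covers 93.7%. The correct interval is 2.074/1.96 = 1.058 times as wide. If 1.645 were used as the test cutoff, one-sided error would be 5.7%.

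**4. Gain from adjustment, equal SDs.** Let σ be the SD at each time.
- Variance of d = 2σ²(1 − rho), held at 16.
- Residual variance after adjustment = σ²(1 − rho²).
- Ratio = (1 + rho)/2.
- Estimating the slope multiplies the variance by about 1 + 1/(24 − 4) = 1.05.
- Break-even: (1 + rho)/2 = 1/1.05, so rho ≈ 0.905.

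| rho | (1 + rho)/2 × 1.05 | Adjusted power (t, 21 df) | Change-score power |
|---|---|---|---|
| 0.3 | 0.683 | 89% | 77% |
| 0.5 | 0.788 | 85% | 77% |
| 0.7 | 0.893 | 81% | 77% |
| 0.8 | 0.945 | 79% | 77% |
| 0.9 | 0.998 | 77% | 77% |

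At rho 0.95 the adjusted power is 75.6%, a loss of about 1 point.

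**5. Larger day-7 SD in the active arm only** (average change variance held at 16):

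| rho | 1.5 times | 2 times |
|---|---|---|
| 0.3 | 83.0% | 79.2% |
| 0.5 | 78.8% | 76.1% |
| 0.7 | 75.3% | 75.0% |
| 0.8 | 74.9% | 76.2% |
| 0.9 | 76.5% | 81.0% |

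Against 76.7%, this runs from 1.8 points lost to 6.3 gained, and adjustment is lower in 6 of 10 cases. If the SD grows in both arms, the worst case is 74.8%, a loss of 1.9 points. Over all 25 normal cases (equal SDs, active arm only, both arms), adjustment is lower in 11 and more than 5 points higher in 6. Type I error of the adjusted test was 4.8% to 5.4%.

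**6. Skewed data.** Lognormal data with a multiplicative effect were simulated at log-SD 0.3, 0.5 and 0.8, rho 0.3 to 0.9, and active-arm log-SD 1 or 1.5 times. On the raw scale, adjusted minus change-score power runs from −3.9 to +7.5 points, and the adjusted estimate averages 83% to 99.7% of the true difference. On the log scale it averages 99.6% to 100.5%. This is why the scale must be settled first.

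**The case against.** The strongest reply is that nothing is broken and the payoff is unknown. That stands in part. The estimate is unbiased, the documents give neither rho nor separate SDs, and adjustment loses slightly in many plausible settings. The gain must therefore be called possible, not expected. It is still more than a matter of taste: with normal data the worst simulated loss is about 2 points, while the gain at low to moderate rho with equal SDs is 4 to 12 points.

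A second reply is that a log scale is not just wording, because the endpoint is an arithmetic difference and the sample size is powered as 4/4 on that scale. This is correct, and the fix allows for it.

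Four stronger readings are tempting, and the documents do not support them.

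- **Chance baseline imbalance biases the result.** A one-standard-error imbalance shifts the change-score estimate by (1 − rho) × [4/√(2(1 − rho))] × √(2/12) with equal SDs. That is 0.82 at rho 0.5, against a standard error of 4 × √(2/12) = 1.63. This variation is already inside sedif; it is the efficiency point again, not bias.
- **Adjustment could add 16.5 points.** One simulated case does (93.2%). It needs the day-7 SD to double in both arms, placebo included, at rho 0.9. Nothing in the plan suggests that.
- **Earlier responder data predict a gain.** Section 2.2.2 reports a response in the "rectum in two of three patients receiving the active GCC agonist", but for a different agonist, in three people, after oral bowel preparation. The same section reports no rectal response with enema preparation, which this trial uses. It cannot anchor a power claim.
- **The whole planned analysis is valid as printed.** The contrast is unbiased, but the 1.96 interval is somewhat too narrow.

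**Conclusion.** The point holds as an optional improvement. Section 13.4 uses baseline only by subtraction. The contrast is unbiased, provided both biopsies are obtained from those randomized, since Section 13.8 limits the evaluable set to people with both. The printed interval covers about 93.7% under normality and equal variances.

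With the plan's difference and SD of 4 and equal SDs, adjustment takes power from about 77% to between 89% and 77% as rho rises from 0.3 to 0.9. With more day-7 spread in the active arm only, the change is about −2 to +6 points. These are assumed ranges; the documents fix neither the size nor the sign. Adjustment on a skewed raw scale is not advised as the primary analysis.

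The 8-versus-2 biopsy conflict is separate. It matters here because the divisors in Section 13.4 and the noise in the baseline mean depend on that number. With independent replicates, the biopsy-level variance of a mean of 2 is 8/2 = 4 times that of a mean of 8, which would both lower rho and raise the SD of the change.

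**What to change.** Before unblinding, amend Section 13.4 as follows.

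1. **Fix the scale.** Name it outright. A normality pretest is a weak guide here: Shapiro-Wilk at 5% on 24 lognormal values detects skew in about 30% of trials at log-SD 0.3 and 61% at 0.5. If log cGMP is chosen, restate the endpoint as a ratio effect and restate the sample-size basis.
2. **Primary estimate.** On that scale, use the arm coefficient from a linear model of day-7 mean cGMP on arm and baseline mean cGMP, with t-based test and interval on 21 df.
3. **Supporting analysis.** Keep the unadjusted difference in mean change, with a t quantile (2.074 on 22 df) in place of 1.96.
4. **Exception.** If skewed data are to stay on the raw scale, reverse the roles: change score primary, adjusted model supporting.
5. **Separately,** reconcile the number of biopsies averaged in Section 13.4 with the number assayed in Section 10.2, and correct the divisors to match.

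**Cost.** Items 1 to 4 need no new data, procedures or participants. On the current scale they are wording only; a log scale also means rewriting the endpoint and its power statement. Item 5 is also wording, unless reconciling it changes how many biopsies are assayed. The statistical price is one degree of freedom, up to about 2 points of power with normal data, and about 4 points plus a small-sample bias if the adjusted model is used on skewed raw data.

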### **5.1 Dose Regimen and Dose Groups**

We will test 27 mg dolcanatide daily for 1 week (7 days), enrolling 24 participants total (12 on active agent and 12 on placebo), to test the hypothesis that a pharmacological effect on cGMP levels can be detected by flexible sigmoidoscopy following PEG enema for dolcanatide vs. placebo. Ultimately, the goal is to determine whether or not 27 mg dolcanatide produces a pharmacological effect on cGMP levels in rectal mucosa sampled by sigmoidoscopy. All participants will undergo sigmoidoscopies at baseline and after seven days of daily dosing with dolcanatide or placebo. For each participant, 8 biopsies will be obtained from the rectum on Day -1 and Day 7. Biopsies will be used to evaluate cGMP levels, and stored for future analyses.

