### **Screening 2**

Participants will be limited to clear liquids until noon and then fast, with free access to water, until the flexible sigmoidoscopy at about 3:00 p.m. Participants will be given PEG enemas about 1.5 hours prior to sigmoidoscopy. Up to 3 enemas may be administered until evacuation is clear. PEG enemas are being used because they have been demonstrated to be optimum for preserving epithelial cell integrity for biopsy and subsequent analyses.

Eight mucosal biopsies will be obtained from 8 discrete areas in the rectum (each separated by no less than 0.5 cm in any direction). In addition, all biopsies will be obtained from areas no less than 0.5 cm above the dentate line. All samples will be flash-frozen in liquid nitrogen and stored at  $-80^{\circ}\text{C}$  for analysis of cGMP.

Following the sigmoidoscopy, a meal will be provided. Medically stable participants can be discharged at the discretion of the investigator, or participants may be kept overnight for prolonged observation for safety. Specifically, participants who are experiencing pain, bleeding, respiratory distress, fever, or other clinical manifestations that might indicate that a complication occurred during the procedures will be observed overnight or until the symptoms resolve.

Incidentally noted endoscopy findings that are felt to be potentially clinically relevant, in the opinion of the endoscopist, will be biopsied for histologic review. Specimens from any incidentally noted findings obtained by sigmoidoscopy will be fixed in formalin (10%) and sent to the Pathology Department at Thomas Jefferson University for diagnostic assessment. The investigator will review findings with study participants and discuss their continuation in the study. Participants will be referred to primary care physicians or gastroenterologists for further diagnosis and therapy, as appropriate, according to institutional standards of good clinical practice.

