#### **7.4 Evaluation at Completion of Study Intervention**

##### **Day 7**

Participants will arrive at the CRU in a fasted state in the morning. Adverse events (AE), concomitant medications, and vital signs will be assessed. Blood will be drawn for safety testing (albumin, total bilirubin, calcium, bicarbonate, chloride, creatinine, glucose, alkaline phosphatase, potassium, total protein, sodium, AST/SGOT, ALT/SGPT, BUN, CBC with differential, PTT and PT/INR), urinalysis, urine drug screen, and a brief physical exam will be performed. An oral dose of dolcanatide or placebo will be administered under direct supervision of the CRU staff at approximately 07:00 a.m. Participants will be limited to clear liquids until 12:00 p.m. and remain fasting thereafter until the scheduled sigmoidoscopy, which will take place approximately 8 hours after the dolcanatide /placebo dose time. Participants will be given the first of a maximum of 3 enemas beginning at approximately 1:30 p.m.

Eight mucosal biopsies will be obtained from 8 discrete areas in the rectum (each separated by no less than 0.5 cm in any direction). In addition, all biopsies will be obtained from areas no less than 0.5 cm above the dentate line. All samples will be flash-frozen in liquid nitrogen and stored at -80°C for analysis of cGMP. Any abnormalities identified during the procedure will be handled and followed according to standards of usual clinical practice. Following the sigmoidoscopy the participants will be discharged to the CRU after recovery. A light meal will be provided. Medically stable participants can be discharged at the discretion of the investigator, or participants may be kept overnight or prolonged observation for safety. Specifically, participants who are experiencing pain, bleeding, respiratory distress, fever, or other clinical manifestations that might indicate that a complication occurred during the procedures will be observed overnight or until the symptoms resolve.

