#### **Estimate the Pharmacodynamic (PD) Response rate across all patients and compare between arms:**

Each participant will be assessed for PD response. The calculation is based on the standardized difference in means for the pharmacological effect on cGMP levels at the participant level, as shown in the following mathematical formulas, where a subject with a  $z \geq 1.645$  will be considered a PD responder. A participant with a  $z < 1.645$  will be considered a non-responder. If the cGMP values are not normally distributed, a transformation to a variable with a normal distribution will be performed. The PD response rate will be compared between the 2 arms using a standard Chi-square or Fisher's exact test. See the detailed calculations below for how the analysis will be done for calculating whether or not a subject is a PD responder:

Let  $i$  index persons and  $z$  index randomization group. For each time (baseline and final) there are 8 biopsies or replicates.

$$\text{Let } x_{zij} = \text{baseline cGMP level for person } i \text{ in randomization group } z \text{ with replicate } j.$$

$$x_{z\text{imean}} = \sum_j x_{zij} / 8 = \text{mean baseline level}$$

$$v_{zi} = \sum_j (x_{zij} - x_{z\text{imean}})^2 / 7 = \text{variance of baseline level for one replicate for person } i \text{ in group } z$$

$$v_{z\text{imean}} = v_{zi} / 8 = \text{variance of mean of baseline replicates for person } i \text{ in group } z$$

Let  $y_{zij}$  = day 7 cGMP level for person  $i$  in randomization group  $z$  and replicate  $j$ .

$$y_{z\text{imean}} = \sum_j y_{zij} / 8 = \text{mean baseline level}$$

$$w_{zi} = \sum_j (y_{zij} - y_{z\text{imean}})^2 / 7 = \text{variance of final level for one replicate for person } i \text{ in group } z$$

$$w_{z\text{imean}} = w_{zi} / 8 = \text{variance of mean of final replicates for person } i \text{ in group } z$$

$$\text{Let } z\text{stat}_{zi} = (y_{z\text{imean}} - x_{z\text{imean}}) / \text{Sqrt}[v_{z\text{imean}} + w_{z\text{imean}}]$$

Define  $PD_{zi}$  an indicator of a statistically significant increase (at one-sided alpha of .05) in mean cGMP from baseline to final result for person  $i$  in group  $z$ .

Let  $PD_{zi} = 1$  if  $z\text{stat}_{zi} \geq 1.645$ , and 0 otherwise.

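### Sections 13.4 and 13.5 average 8 cGMP values per visit, and 7.2 and 7.4 freeze every biopsy, but Section 10.2 freezes 5, assays 2 and fixes 3 in formalin

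*Combined protocol and SAP*

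**What the plan says.** All the relevant sections agree that eight rectal biopsies are taken before and after intervention. They disagree on what happens to them.

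- Section 13.4 (primary endpoint): "The mean cGMP value will be calculated based on 8 biopsies from the rectum assessed at each time point". The formulas divide the sum over replicates by 8 at both visits.
- Section 13.5 (PD response): "For each time (baseline and final) there are 8 biopsies or replicates". Means use divisor 8, replicate variances divisor 7, and variances of the mean divisor 8.
- Section 7.2, Screening 2: after the eight biopsies are described, "All samples will be flash-frozen in liquid nitrogen and stored at" −80°C for cGMP.
- Section 7.4, Day 7: "All samples will be flash-frozen in liquid nitrogen and stored at -80°C for analysis of cGMP".
- Section 10.2: five biopsies are frozen; "Among the 5 biopsies, 2 of them will be evaluated for cGMP concentration"; and "3 biopsies will be flattened immediately and fixed in 10% formalin within 2 min of collection", for possible Ki67 work.
- Section 5.1 gives no count: "Biopsies will be used to evaluate cGMP levels, and stored for future analyses".

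Sections 8.1 and 8.2 refer the reader to 13.4 and 13.5 for the endpoints, and Section 13.8 refers to 13.4 for response. None of them mentions the handling of tissue.

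**The concern.** cGMP in rectal tissue is the only primary measurement, and the plan gives two incompatible instructions for producing it. Endoscopy staff who follow Sections 7.2 and 7.4 freeze eight samples; those who follow Section 10.2 put three into formalin within two minutes, which cannot be undone. The laboratory is told to assay two, while the analyst is given formulas for eight. If this is left open, the number assayed may vary between participants or be chosen late, and the analyst must replace the primary formula with one the plan does not state. The precision of each participant's mean, and so the planned power, may also differ from what was assumed.

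**Working it through.** **1. The plan's own figure.** Inputs from Section 13.4: one-sided alpha 0.05 (1.645), power 80% (0.84), difference 4, SD 4, 12 per arm.

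N = (1.645 + 0.84)² × (32/16) = 6.175 × 2 = 12.35, rounded in the plan to 12. This reproduces.

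Power at 12 per arm by the same normal formula: Φ(4 / (4 × √(2/12)) − 1.645) = Φ(2.449 − 1.645) = Φ(0.804) = 79%.

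The calculation has no term for the number of biopsies, so it reproduces under either handling rule and cannot show which was intended.

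**2. Counts side by side, per visit.**

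| Section | Frozen | Formalin | cGMP values |
|---|---|---|---|
| 7.2, 7.4 | all 8 | none | frozen for cGMP; number assayed not given |
| 10.2 | 5 | 3 | 2 |
| 13.4, 13.5 | – | – | 8 |

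Even if every frozen sample under Section 10.2 were assayed, there would be 5 values, not 8.

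**3. The stated formulas with two values.** Let M be the true mean of the two results and SS their sum of squares about M.

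- Section 13.4: the computed visit mean is 2M/8 = M/4. Each participant's change, the arm difference and its confidence limits all come out at a quarter of their correct size. The ratio of difference to standard error is unchanged if this is done everywhere.
- Section 13.5: deviations are taken from M/4, so their sum of squares is SS + 2(M − M/4)² = SS + 1.125M². Dividing by 7 and then 8 gives (SS + 1.125M²)/56, where the variance of a two-value mean should be SS/2. The cGMP level itself enters the variance, so the responder statistic is distorted, not just rescaled.

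**4. Illustration for power.** The documents give neither the number of assayed biopsies behind SD 4 (call it m₀) nor the share f of that variance that is biopsy-to-biopsy. Both are assumptions here. With m assayed:

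Var(d) = 16 × [(1 − f) + m₀f/m]; power = Φ(4 / (SD × √(2/12)) − 1.645); N = 12.35 × SD²/16.

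For m₀ = 8 and m = 2, Var(d) = 16(1 + 3f):

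| f (assumed) | SD | Power at 12 per arm | N per arm, plan's formula |
|---|---|---|---|
| 0 | 4.00 | 79% | 12.35 |
| 10% | 4.56 | 69% | 16.1 |
| 25% | 5.29 | 58% | 21.6 |
| 50% | 6.32 | 46% | 30.9 |

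For m₀ = 2 and m = 2 there is no loss (79%). For m₀ = 2 and m = 8 power rises to 82%, 86% or 93% for the same three shares.

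**The case against.** The formulas are unusable only in a literal sense: change the divisors and a mean and variance can be computed from any m of at least 2. That is right, and it is why the correction is one of wording. It does not say which m was meant.

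Sections 8.1, 8.2 and 13.8 do point to 13.4 and 13.5, so one can argue that the statistical section governs. That stands for the endpoint definition. It does not settle tissue handling: Section 10.2 is the specimen instruction, and nothing tells staff to disregard it. Nor can the 8 in Section 13.4 be read as biopsies merely collected, because the sentence says assessed and the formulas index cGMP values by replicate.

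The power effect is not established. Across the scenarios above it runs from 46% to 93%, driven by two quantities the documents do not give. This stands, and the figures are illustration only.

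A reader might also infer that the responder cutoff of 1.645, described in Section 13.5 as "an indicator of a statistically significant increase (at one-sided alpha of .05) in mean cGMP from baseline to final result", has a false-responder rate set by the number assayed, and that two biopsies must be worse than eight. The documents do not support that. Such a calculation assumes that a participant's true level does not move between visits, so that all variation is between biopsies. Under the variance model of step 4 (m₀ = 8, no mean change), the share passing 1.645 would be 23%, 17% and 14% with two biopsies and 31%, 21% and 13% with eight, for f of 10%, 25% and 50%. The ordering reverses at the smaller shares, so m alone does not determine the rate.

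**Conclusion.** The point holds as a contradiction in current text, and that part needs no assumption. Sections 7.2 and 7.4 cannot be followed together with 10.2, and Sections 13.4 and 13.5 need eight values where 10.2 supplies two. With two values the stated primary mean is a quarter of the correct one. It must be corrected, and because fixation is irreversible, the freeze/formalin part must be corrected before the first biopsy.

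The size of any power loss is conditional. It is 10, 21 or 33 percentage points (79% to 69%, 58% or 46%) if SD 4 describes 8-biopsy means, two are assayed, and the biopsy share is 10%, 25% or 50%; it is nil if SD 4 already describes 2-biopsy means.

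A reader might infer that the trial is underpowered because the earlier study collected eight biopsies per site. Section 2.2.2 reports how many were collected, not how many were assayed for cGMP, and it and Section 14.7 also report VASP and Ki67 work in that study. The basis of SD 4 is therefore unknown.

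**What to change.** Reconcile Sections 7.2, 7.4, 10.2, 13.4 and 13.5 to one set of numbers per visit: frozen, fixed in formalin, and assayed for cGMP (m). Settle the freeze/formalin split before any collection. The value of m can wait until before the first assay, because frozen samples are archived at −80°C (Section 9.1).

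Replace the replicate divisor 8 with m in Sections 13.4 and 13.5, and the divisor 7 with m − 1 in Section 13.5, the only place it occurs. State how many assayed biopsies lie behind the planning SD of 4, and restate power if that number differs from m.

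The reconciliation is wording only, with no new biopsies or participants. The choice of m has its own cost. For 24 participants and two visits the assays number 24 × 2 × m = 96, 240 or 384 for m = 2, 5 or 8. The assay consumes tissue (Section 9.1). With the split in Section 10.2, m = 5 leaves no frozen biopsy for VASP work (Section 2.5) or banking (Section 10.4), and m = 8 also removes the formalin tissue reserved for Ki67.
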